## 9.6. FST Timing

Subjects will be assigned to FST Timing (random assignment) according to their age:

## FST Timing for 14-80 years old:

Group	Sensor Wear Day Timing of FST from Sensor Insertion T=0	
A1	Day 1, 3, 4 and 7	2-10 hours (+2), 50-58 hours (±6), 74-82 hours (±6), 146-154 hours (±6)
A2	Day 1, 3, 4 and 7	10-18 hours (±2), 58-66 hours (±6), 82-90 hours (±6), 154-162 hours (±6)
B1	Day 1, 3, 4 and 7	18-26 hours (±2), 66-74 hours (±6), 90-98 hours (±6), 162-170 hours (-6, +2)
B2	Day 2, 4, 5 and 6	24-32 hours (±2), 74-82 hours (±6), 98-106 hours (±6), 122-130 hours (±6)
C1	Day 2, 4, 5 and 6	32-40 hours (±2), 82-90 hours (±6), 106-114 hours (±6), 130-138 hours (±6)
C2	Day 2, 4, 5 and 6	40-48 hours (±2), 90-98 hours (±6), 114-122 hours (±6), 138-146 hours (±6)

## FST Timing for 7-13 years old:

Group	Sensor Wear Day	Timing of FST from Sensor Insertion T=0
A1	Day 1, 7	2-8 hours (+2), 146-152 hours (±6)
A2	Day 1, 7	20- 26 hours (±2), 164-170 hours (-6, +2)
B1	Day 2, 5	26-32 hours (±2), 116-122 hours (±6)
B2	Day 2, 5	44-50 hours (±2), 98-104 hours (±6)

10976639DOC Version D Page 57 of 170

Medtronic

Group	Sensor Wear Day	Timing of FST from Sensor Insertion T=0
C1	Day 3, 5	50-56 hours (±6), 116-122 hours (±6)
C2	Day 3, 5	68-74 hours (±6), 98-104 hours (±6)
D1	Day 4, 6	74 -80 hours (±6), 140-146 hours (±6)
D2	Day 4, 6	92-98 hours (±6), 122-128 hours (±6)

## FST Timing for 2-6 years old:

Group	Sensor Wear Day	Timing of FST from Sensor Insertion T=0
A1	Day 1, 7	2-6 hours (+2), 148-152 hours (±6)
A2	Day 1, 7	20- 24 hours (±2), 166-170 hours (-6, +2)
B1	Day 2, 5	26-30 hours (±2), 118-122 hours (±6)
B2	Day 2, 5	44-48 hours (±2), 100-104 hours (±6)
C1	Day 3, 5	50-54 hours (±6), 118-122 hours (±6)
C2	Day 3, 5	68-72 hours (±6), 100-104 hours (±6)
D1	Day 4, 6	74 -78 hours (±6), 142-146 hours (±6)
D2	Day 4, 6	92-96 hours (±6), 124-128 hours (±6)

## The following is the FST schedule for the subjects according to their age: Subjects 14 - 80 years

- 4 x 8 hours FST
- Challenges
  - Two Hyperglycemic Challenges

10976639DOC Version D Page 58 of 170

- Two Hypoglycemic Challenges
- If challenges are performed, the following are recommended:
  - **US only:** Investigator discretion may be used in selecting which challenge is to be performed for each FST as long as 2 hyperglycemic challenges and 2 hypoglycemic challenges are met.
  - **China only:** Whether performing recommended challenges or not will be based on Ethics Committee (EC) suggestion and investigator discretion. Absence of challenges during FST will not be considered a protocol deviation.

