## 6. Study Design

The study is a multi-center, prospective, single-arm study without controls, and random assignments of sensor location, frequent sample testing (FST) day, and FST time.

For the Study Design, refer to:

- Section 10.1 for Subjects 14-80 years Study Design
- Section 11.1 for Subjects 2-13 years Study Design

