#### **10.2.1.6.4.1** Blood Glucose Monitoring During the YSI™\* FST

The frequency of blood draws for YSI™\* FST sampling is dependent on the average value of YSI-B and YSI-W probes of the previous sample, according to the following ranges:

- less than (<) 75 mg/dL (4.2 mmol/L); every 5 minutes (window of 3-8 minutes)
- greater than or equal to (≥) 75 mg/dL (4.2 mmol/L); every 15 minutes (window of 7-23 minutes)

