#### **Hypoglycemic and Hyperglycemic Challenges**

#### Subjects 2 - 13 years:

During the day of FST, subjects will not participate in hypoglycemic and hyperglycemic challenges.

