### 20. Stopping Rules

#### 20.1.1. Stopping Rules for Subjects for FST

- Maximum blood volume drawn:
  - 4 mL/kg (inclusive of all YSI™\* FST days) during this study or 400 cc whichever is more for subjects' age 14-80 years old. However, no more than 3 mL/kg of blood volume in a 24-hour period is to be drawn.
  - 4 mL/kg (inclusive of all YSI™\* FST days) during this study for subjects' age 7-13 years old.
  - o 50 mL will be maximum blood volume for subjects' age 2-6 years old during the study. However, no more than 1 mL/kg of blood volume in a 24-hour period is to be drawn.

Please note that the time of the 24-hour blood draw limit would begin at the start of the first blood draw of an FST and end 24 hours after that. Because patients may have FSTs on two consecutive days (Day 3 and Day 4 or Day 4 and Day 5), please be careful not to exceed the 24-hour blood draw volume maximum. For example, when FSTs occur on two consecutive days it may be preferable to have a hyperglycemic challenge on one day and then a hypoglycemic challenge on the subsequent day, or vice versa, in subjects who may be more likely to reach the maximum 24-hour blood draw volume.

- Severe hypoglycemia (see severe hypoglycemia definition Section 22.1). Subject may continue in study (including observational FST) but not participate in any more challenges.
- Glucose greater than (>) 500 mg/dL (27.8 mmol/L) during challenge. Subject may continue in study (including observational FST) but not participate in any more challenges.
- Ketone greater than or equal (≥) to 3 mmol/L regardless of BG during challenge. Subject may continue in study (including observational FST) but not participate in any more challenges.

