### 2) Statistical analysis

Summary statistics (N, %) for each of the zones, as well as combined Zones A and B, will be calculated.

In order to evaluate differing levels of accuracy at various YSITM\* defined glucose levels, the number and percentage of paired observations falling into Zones A, B, A+B, C, D, and E will be provided by YSITM\* glucose ranges of 40-80 mg/dL (2.2 - 4.4 mmol/L), greater than (>) 80-120 mg/dL (4.4 - 6.7 mmol/L), greater than (>) 120-240 mg/dL (6.7 - 13.3 mmol/L), and greater than (>) 240 mg/dL (13.3 mmol/L).

All analysis performed using the Clarke Error Grid comparing the paired sensor and YSI™\* reference glucose values will be duplicated using the Continuous Error Grid [Clarke et al, 1987] and the Consensus Error Grid [Parkes et al, 2000].

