7.9.1.3 Agreement, ARD, Bias (Accuracy Analyses)

The following will be evaluated for each of the 3 primary and 15 secondary datasets.

The agreement, ARD (the absolute differences), and bias between the sensor and YSI[™]* relative to the YSI[™]* reference, will be calculated for each day separately. Summary statistics will include its mean, standard deviation, min, median, and max.

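### US investigators choose which glucose challenge falls on which wear day, and accuracy is reported per day with no glucose-range split, so a difference between days can reflect the challenge mix rather than the sensor.

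*Protocol*

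**What the plan says.** Protocol Section 6 lists what is randomised: "random assignments of sensor location, frequent sample testing (FST) day, and FST time". Challenge type is not on that list. Protocol 9.6 gives subjects aged 14-80 four 8-hour FSTs with two hyperglycemic and two hypoglycemic challenges. In the US, "Investigator discretion may be used in selecting which challenge is to be performed for each FST", as long as that total is met. In China, "Whether performing recommended challenges or not will be based on Ethics Committee (EC) suggestion and investigator discretion". At ages 2-13, "subjects will not participate in hypoglycemic and hyperglycemic challenges" (Protocol 11.1). Subjects aged 14-80 without a known insulin-carbohydrate ratio and sensitivity factor are only observed (Protocol 10.2.1.6.4.4).

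Two rules in Protocol 20.1.1 bear on the order. Where FSTs fall on consecutive days, "it may be preferable to have a hyperglycemic challenge on one day and then a hypoglycemic challenge on the subsequent day", or the reverse, in subjects more likely to reach the blood-volume limit. Severe hypoglycemia, or glucose above 500 mg/dL or ketones of 3 mmol/L or more during a challenge, bars the subject from further challenges, though observational FSTs may continue.

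On analysis, SAP 7.9.1.3 (and Protocol 25.9.3) says that agreement, ARD and bias "will be calculated for each day separately". This applies to all 3 primary and 15 secondary datasets, with no split by glucose range or challenge. Outputs that are split by range, namely the error grids by YSI range (SAP 7.9.1.4.3) and the iCGM endpoints by SG range (SAP 7.9.1.2.2), are not split by day. The subgroups in SAP 7.9.1.4.6 include neither challenge type nor wear day by range.

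**The concern.** The objective is accuracy over 7 days, and the per-day table is the only planned in-clinic accuracy output by wear day. A reader will use it to see whether the sensor holds up from first to last day.

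The challenge sets both the glucose range of an FST and its sampling rate, since draws are every 5 minutes below 75 mg/dL and every 15 minutes otherwise (Protocol 10.2.1.6.4.1). The agreement rule also changes with level: ±20 mg/dL when SG is below 80, and 20% otherwise. ARD depends on level too, because it is relative to YSI. As an illustration, a 10 mg/dL error is 10/60 = 16.7% at 60 mg/dL and 10/200 = 5% at 200 mg/dL.

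The two-and-two rule balances each subject's total, not the days. Four FSTs with two of each type can be ordered in 4!/(2! × 2!) = 6 ways. In groups A1, A2 and B1 (Days 1, 3, 4 and 7), a subject who alternates on Days 3 and 4 has one of each type left, so Days 1 and 7 get opposite challenges, in an order that the site decides. The stopping rules can also remove challenges from later FSTs, which changes the mix with wear day without any site habit. A real change on Day 1 or Day 7 could then be masked, or an apparent one created.

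**Working it through.** The documents give no per-day or range-specific agreement rate, so there is no stated figure to reproduce. The check asks how far a day's rate can move with the sensor held constant.

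**Inputs.** A hypoglycemic challenge aims for about 2 hours below 70 mg/dL, and a hyperglycemic one for about 2.5 hours at 180-400 mg/dL (Protocol 10.2.1.6.4.4). Each FST lasts 8 hours, with the sampling intervals given above. I assume that targets are met, that every draw yields a pair, and that there are no lows outside the challenge.

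**Pairs per FST.**
- Hypoglycemic: 120/5 = 24 low pairs plus 360/15 = 24 others, so 48 pairs, 50% low.
- Hyperglycemic: 480/15 = 32 pairs, none low; 150/15 = 10 of them (31%) are in the high range.
- Observation only, glucose staying at 75 mg/dL or above: 480/15 = 32 pairs, none low.

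**Low share of a day's pairs.** If a fraction h of that day's FSTs is hypoglycemic and the rest hyperglycemic, the low share is 24h / (48h + 32(1 - h)) = 24h / (32 + 16h).
- h = 0: 0%
- h = 0.25: 6/36 = 16.7%
- h = 0.40: 9.6/38.4 = 25.0%
- h = 0.60: 14.4/41.6 = 34.6%
- h = 0.75: 18/44 = 40.9%
- h = 1: 24/48 = 50%

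**Shift between two days.** Shift = (difference in low share) × (difference in agreement between the low range and the rest). The agreement difference is an assumption, taken over 0 to 15 points.

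| Hypoglycemic share, day against day | Low-share difference | 0 points | 5 points | 10 points | 15 points |
|---|---|---|---|---|---|
| 50% v 50% | 0 | 0 | 0 | 0 | 0 |
| 60% v 40% | 9.6% | 0 | 0.5 | 1.0 | 1.4 |
| 75% v 25% | 24.2% | 0 | 1.2 | 2.4 | 3.6 |
| 100% v 0% | 50% | 0 | 2.5 | 5.0 | 7.5 |

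If the high range is also allowed to differ (assumed agreement of 80% low, 87% middle and 93% high), the three unequal mixes give 1.0, 2.6 and 5.4 points. If low-range agreement were better rather than worse, the shifts in the table would keep their size and change sign. Within a glucose range, or at one common range mix, the artificial shift in this calculation is 0.

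**The case against.** The strongest reply is that nothing inferential is at stake. Pass or fail rests on a GEE test of pairs pooled over days against 75%. The per-day output is summary statistics, and the documents state no Day 1 versus Day 7 hypothesis. This stands: the concern is about how wear-day results are described, not about the primary test.

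A reader might infer that wear day and challenge are inseparable in this trial. The documents do not support that. All YSI values are retained (Protocol 25.8.3), so each pair can be classified by day and by reference glucose. It is the planned tables that fail to separate them, not the data.

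A reader might also infer that sites will follow a systematic order. Nothing shows this. The advice in Protocol 20.1.1 is conditional and allows either order, and opposite orders cancel across subjects. The protocol also accepts that challenge targets may not always be met, so the target-based pair counts are idealised.

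Scope is limited as well. In primary Datasets 2 and 3 only the 14-17 part can have challenges. In the combined US and China report, 40 of the 140 planned adult completers are in China, where challenges are optional.

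What survives is that challenge type is left free by wear day, the stopping rules act in one direction over time, and no planned output would show whether the mix differed.

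**Conclusion.** The point holds as a limit on the per-day accuracy description for challenge participants aged 14-80, chiefly adult Dataset 1. As specified, that description mixes wear day with challenge mix. A distortion needs two things together: a mix that differs by day, and accuracy that differs by glucose range. The documents establish neither and rule out neither.

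Under the assumed gap, a moderate imbalance (60/40) costs about 0.5-1.4 points and a strong one (75/25) 1.2-3.6. The 2.5-7.5 range should not be read as the expected effect, because it needs every subject to follow the same order and every target to be met. This is a worthwhile, cheap improvement, not a flaw in the primary analysis.

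**What to change.** For the primary datasets, and at least Dataset 1, add three outputs to SAP 7.9.1.3 and Protocol 25.9.3:

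1. Agreement, ARD and bias by wear day within YSI reference ranges, with the number of pairs in each cell. The four ranges already used for the error grid would serve (40-80, above 80 to 120, above 120 to 240, and above 240 mg/dL), with a stated rule for YSI below 40.
2. A by-day agreement rate standardised to one common YSI-range mix: the sum over ranges of (common share of pairs) × (that day's agreement in the range). State the common mix in advance, for example the pooled mix over all days.
3. A table of challenge type (hypoglycemic, hyperglycemic, observation) by wear day.

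Use YSI rather than SG ranges. The challenges and the sampling rule act on blood glucose, and a drifting sensor would move pairs between SG ranges and so hide part of the change being sought. Base any statement comparing accuracy between wear days on these outputs. Leave the pooled primary analysis, the clinical procedures and investigator discretion as they are.

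The cost is SAP wording and tables from data already collected. Seven days by four ranges is 28 cells per metric per dataset, and some will be small, which is why the pair counts are needed. Extending the tables to all 18 datasets would give 504 cells per metric, so limiting them to the primary datasets is sensible.

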## Subjects 7 - 13 years

2 x 6 hours FST

### Subjects 2 - 6 years

- 2 x 4 hours FST
- SMBG only

Once subject is assigned to the study group (if applicable), subjects will stay in that randomly assigned group during the study.

## 9.7. Treatment Assignment

Investigational centers will receive random assignment (sensor location) from Medtronic.

Subjects will be assigned to sensor location (random assignment) according to their age:

- Subjects 14 80 years
  - 14-17 years
    - Arm/Arm/Buttock
    - Buttock/Buttock/Arm
  - 18-80 years
    - Arm/Arm

### Subjects 7 - 13 years

- Arm/Arm/Buttock
- Buttock/Buttock/Arm

## CIP330 Clinical Investigation Plan 10976639DOC Version D Page 59 of 170 Medtronic

## Subjects 2 - 6 years

- Arm/Buttock
- Subjects 2-6 years old may have their parent, guardian, or legally authorized representative choose the area for their sensor placement.

## 10. Subjects 14-80 Years Study Design and Study Procedures

This section is presented as below:

Section 10.1: Study Design

• Section 10.2: Study Procedures (Subjects 14-80 years)

[figure not shown]
## 10.1. Study Design

The study is a multi-center, prospective, single-arm study without controls, and random assignments of sensor location, frequent sample testing (FST) day, and FST time.

Subjects will wear sensors in the following configurations and follow the FST schedule:

- Sensor Location
  - 14-17 years
    - Arm/Arm/Buttock
    - Buttock/Buttock/Arm
  - 18-80 years
    - Arm/Arm
- o FST Schedule
  - 4 x 8 hours FST
  - Challenges
    - Two Hyperglycemic Challenges
    - Two Hypoglycemic Challenges
    - If challenges are performed, the following are recommended:

10976639DOC Version D Page 61 of 170

- US only: Investigator discretion may be used in selecting which challenge is to be performed for each FST as long as 2 hyperglycemic challenges and 2 hypoglycemic challenges are met.
- China only: Whether performing recommended challenges or not will be based on Ethics Committee (EC) suggestion and investigator discretion. Absence of challenges during FST will not be considered a protocol deviation.

Subjects will be assigned to FST Timing (random assignment) according to their age:

## FST Timing for 14-80 years old:

Group	Sensor Wear Day Timing of FST from Sensor Insertion T=0	
A1	Day 1, 3, 4 and 7	2-10 hours (+2), 50-58 hours (±6), 74-82 hours (±6), 146-154 hours (±6)
A2	Day 1, 3, 4 and 7	10-18 hours (±2), 58-66 hours (±6), 82-90 hours (±6), 154-162 hours (±6)
B1	Day 1, 3, 4 and 7	18-26 hours (±2), 66-74 hours (±6), 90-98 hours (±6), 162-170 hours (-6, +2)
B2	Day 2, 4, 5 and 6	24-32 hours (±2), 74-82 hours (±6), 98-106 hours (±6), 122-130 hours (±6)
C1	Day 2, 4, 5 and 6	32-40 hours (±2), 82-90 hours (±6), 106-114 hours (±6), 130-138 hours (±6)
C2	Day 2, 4, 5 and 6	40-48 hours (±2), 90-98 hours (±6), 114-122 hours (±6), 138-146 hours (±6)

Sensors worn in the same insertion site location may be inserted on same side or opposite sides. Sensors may be inserted with the assistance of a caretaker.

Subjects will continue with their current diabetes regimen independent of the study devices. Subjects will be instructed by the investigational center that they are not to use the study devices (except for the study meter) for the management of their diabetes.

Subjects will wear the devices up to 7-day training period, followed by a 7-day study period. Investigational center staff will ensure 176-188 hours of sensor wear (sensors may be removed at that time or after that time to ensure that the devices are not removed pre-maturely). In the event that early sensor removal occurs during the training period, the subject can continue to the study period based on PI discretion.

During the study period, each subject will undergo four YSI™\* FSTs.

During the YSI™\* FST, intravenous (IV) blood samples will be drawn every 5-15 minutes and analyzed using the YSI™\*.

# CIP330 Clinical Investigation Plan 10976639DOC Version D Page 62 of 170 Medtronic

The YSI™\* FST will be approximately 8 hours during the in-clinic visit. For details on maximum amount of blood drawn refer to Synopsis and Stopping Rules for Subjects for FST (section 20.1.1).

For device troubleshooting and device complaints (See Section 24):

- **US only:** Subjects and/or Sites are to call the 24-Hour Technical Support (TS)
- China only: Subjects are to call Investigational Center staff

#### **Hypoglycemic and Hyperglycemic Challenges:**

US only: During the YSI™\* FST, subjects with a known insulin sensitivity factor and insulin carbohydrate ratio will undergo hypoglycemic and hyperglycemic challenges.

**China only:** Whether performing recommended challenges or not will be based on EC suggestion and investigator discretion. Absence of challenges during FST will not be considered a protocol deviation.

## 10.2. Study Procedures (Subjects 14-80 years)

## 10.2.1. Schedule of Events

#### 10.2.1.1. Visit Schedule & Scheduled Follow-up Visit Windows

Each subject's participation will include the following visits (depending on randomly assigned group). The intent is for subjects to wear the study sensors and perform 4 YSI™\* FSTs.

One rescheduled visit can occur during the study period if primary sensors dislodges and new sensors must be reinserted (See Replacement Sensors Sections 13 and 14).

If subject exits the study early (i.e. before their last scheduled visit), all requirements that apply to the final visit should be completed if possible.

## Screening and Training Period: To be completed in 30 days (Visit 1 to Visit 3)

- Visit 1: Consent and Screening
- Visit 2: Study, Device Training and Random Assignment
  - Confirm eligibility. Note that Hct eligibility criteria must be confirmed prior to Visit 2.
  - o Visit 1 and 2 can be combined if eligibility criteria are met (see note above on Hct).
- Visit 3: End of Training Period Investigational center Visit

10976639DOC Version D

Page 63 of 170

[figure not shown]
Medtronic

#### Start of Study Period: To be completed in 60 days from Visit 4 to Visit 12

- Visit 4: Phone Visit or Optional Office Visit
  - **Group A1** May be combined with Visit 5 (e.g., if sensor insertion for Day 1 is done at Visit 5)
  - **Group A2,B1, B2, C1 and C2-**Investigational center must confirm that the sensor insertion was performed at the appropriate insertion time, insertion location, and SMBG reminder.
- Visit 5: YSI™\* 1st FST
- Visit 6: Follow Up Phone Call
- Visit 7: YSI™\* 2nd FST
- Visit 8: Follow Up Phone Call
- Visit 9: YSI™\* 3rd FST
- Visit 10: Follow Up Phone Call
- Visit 11: YSI™\* 4th FST
- Visit 12: End of Study Period Visit
  - Subject has worn sensors for T= 176-188 hours.
  - Visit 11 and Visit 12 may be combined (e.g., FST occurs on Day 7 and end of the sensor wear)
  - Subjects who have new or unresolved adverse event(s) from device-related skin reactions should schedule a follow up visit 3-7 days after Visit 12.
- Unscheduled Visit: For AE Follow Up, if Required (3-7 days after Visit 12)
  - Assess for adverse events, including adverse event from device-related skin reaction ongoing at Visit 12.
  - Update adverse event form or fill in new adverse event form, as applicable.

Figure 2. Visit Schedule Subjects 14-80 years

## 10.2.1.2. Visit 1: Consent and Screening

#### **Overview General**

[figure not shown]
### **Investigational center staff will:**

- US only: Obtain California Experimental Subject's Bill of Rights (if applicable), ICF and assent form (if applicable), and HIPAA form from the subjects
- **China only**: Obtain ICF and assent form (if applicable) from the subjects
- Assess subject eligibility to participate in the study
- Obtain demographic and baseline characteristics including:
  - Age
  - o Gender
  - o Race
  - Ethnicity
  - Prior medical history, to include diabetes classification (e.g., type 1, type 2) and date of diabetes diagnosis
  - Height and Weight

Note: Body mass index (BMI) will be calculated automatically in the study database, based on height and weight measurements entered.

- Concomitant medications (Screening Only)
- CGM experience
- Pump experience
- Total Daily Dose (TDD), if applicable
- Daily basal amount, if applicable
- Time of day basal/long acting insulin is delivered, if applicable
- Insulin carbohydrate ratio and insulin sensitivity factor for subject's insulin requirement, if applicable
- Complete required screening tests, if all eligibility criteria are met:
  - US only: Perform urine test for pregnancy, female subjects of child-bearing age or capability
  - Obtain blood sample:
    - Pregnancy (China only): Perform blood test for pregnancy, female subjects of childbearing age or capability. Send to investigational center's lab for required screening tests.
    - Hct

10976639DOC Version D

 If patient has prior Hct from routine care done within 6 months of enrollment and the report of lab placed with subject source documents, then no blood test needs to be done.

Page 66 of 170

- o **Note:** For all out of range lab results, a single re-test is permitted
- US only: Send to Central Laboratory or local lab for required screening tests. There is no point of care (POC) testing for Hct.
- China only: Send to investigational center's lab for required screening tests.
- Obtain blood sample for Glycosylated hemoglobin (HbA1c) (not an eligibility criteria)
  - US only: Send to Central Laboratory
  - China only: Send to investigational's center lab
- Per Investigator's discretion, subjects may exercise. Subjects will be asked to exercise for a minimum of 30 minutes a day during the YSI™\* FSTs.
- Enter data into electronic Case Report Forms (eCRF)s as appropriate
- Schedule next visit date and time

The study is open to all individuals who meet the eligibility criteria of the study. The investigational center will be responsible for determining adequate source documents to verify subject eligibility. Subjects who do not meet the eligibility requirements for participation in the study will be entered into the database as screen failures. Applicable eCRF(s) will be completed for all subjects and their parent, guardian, or legally authorized representative who signed an ICF and assent form (if applicable), whether they are eligible or ineligible to participate. If a subject fails screening criteria (e.g., Hct or pregnancy test) they will be notified regarding their ineligibility immediately, either in person or via telephone. Eligible subjects will return to the investigational center to begin study and device training at Visit 2.

Visit 2 may be completed on the same day as Visit 1, provided that Hct and pregnancy test results are available and all other eligibility criteria are met.

